5.2. Experimental Procedure Timeline (Figure 1)

During Week 1, enrolled and consented subjects will come to the lab for Week 1 Baseline QST and NCS testing as outlined above. During this baseline testing subjects will be introduced to the QST equipment and will undergo assessment of baseline cold detection threshold (CDT) and vibration detection threshold (VDT), as well as baseline NCS as outlined above. This would take approximately 1.5 hours and both procedures are non-invasive.

Following assessment of Baseline QST and NCS, subjects will be screened for Secondary Exclusion criteria, which relate to their CTS diagnosis and ability to tolerate NCS and QST (**Figure 1**). Subjects who do not pass the Secondary Exclusion Criteria will exit the study, with proper documentation of why they were ineligible.

Those who pass the Secondary Exclusion Criteria will be randomized to MA, LF-EA and HF-EA, as well as undergo random treatment assignment of median (PC3, PC5) or ulnar (HT3, HT4) nerve. Following randomization a subject will undergo acupuncture for 20 minutes involving 2 needles as outlined in detail above.

Following acupuncture, Week 1 Post-acupuncture QST (CDT and VDT) and NCS will be obtained in a manner analogous to the Week 1 Baseline QST and NCS testing outlined above. QST will be obtained first, with the needles retained in position, followed by needle removal and conduction of NCS. This will conclude Week 1. Total estimated time of Week 1 procedures is 4-4.5 hours. Subjects will be provided with water, bathroom break/other breaks as needed and a healthy snack.

Week 2 procedures will occur exactly one week after Week 1, as close to the same time of day as possible. Week 2 will start with Week 2 Baseline QST and NCS testing, following the same methodology as the Week 1 Baseline QST and NCS outlined above, although subjects will not be screened for inclusion/exclusion criteria at Week 2. A second baseline is necessary because in our experience even a single intervention to PC3, PC5 or HT3, HT4 may alter NCS and QST parameters of the median and ulnar nerves, respectively.

Once Week 2 Baseline QST and NCS testing is obtained, acupuncture will be delivered to the nerve not treated during Week 1. For example, if a given subject is randomized to LF-EA and randomly assigned to ulnar nerve acupuncture in Week 1, the same subject will be administered LF-EA to the median nerve in Week 2, following Week 2 Baseline QST and NCS (Figure 1).

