9.4. Statistical Analysis Plan

Primary statistical analysis for all 3 Specific Aims will use linear mixed-effect models to evaluate the effects of treatment group and intervened nerve location on the outcome measures described above. A mixed-model design will be used to create an intention-to-treat framework

and allow for any missing data. Principal assessment will be on the change in outcomes resulting from acupuncture intervention, calculated as the difference in outcomes before and after treatment. These outcomes will include CDT and VDT, distal motor/sensory latencies, CMAP and SNAP amplitudes, CMAP area and duration, nerve conduction velocities (Specific Aim 1). Acupuncture characterization will be carried out first in the Median and Ulnar nerves of the arm (Specific Aims 1, 2). In both Median and Ulnar nerve interventions, group will be a three level factor based on the type of acupuncture - MA, LF-EA and HF-EA (Specific Aim 3).

Specific Aims 1 and 2:

As a principal independent variable, location of the intervention will be a four-level factor encompassing the possible combinations of treated and evaluated nerves. For Specific Aims 1 and 2, these levels will be: MM – Median treated and tested, MU – Median treated and Ulnar tested, UM – Ulnar treated and Median tested, and UU – Ulnar treated and tested. A time variable (Week 1, Week 2) will also be included to test for any effects due to order of the treated nerves. Additional covariates known to be associated with QST and NCS outcomes such as age and gender will be corrected for as well. Secondary analysis will include treatment evaluations of outcomes within each location of intervention and additional contrasts between the four time points (pre and post treatment for both Week 1 and Week 2). Persistence of the acupuncture effects will specifically be assessed by comparing changes in outcomes after the first treatment but before the second session.

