Another way to characterize the wash-out effect of acupuncture is to compare baseline data from Week 1 and Week 2. We will perform an exploratory analysis to assess for an interaction between location and time, in a mixed linear model. We will incorporate nerve location, evaluation time and the location-time interaction to check for dependencies between Week 1 and Week 2. As stated, the dependent outcomes of all models are the change in QST and NCS from baseline to post-acupuncture. This will allow for a full assessment of washout and carry-over effects with respect both to the nerve location (healthy Ulnar vs diseased Median), time (Week 1 vs Week 2) as well as the order of nerve assessment (the interaction). However, with the repeated nerve measures, it will still be necessary to utilize a mixed-model approach so that the random-effects blocking (nerve location dependent on subject) will allow for the intra-subject serial correlation. For the final model, although exploration of the wash-out effect will be critical, it will pose to be impractical to keep all these covariates in the final model. Only significant time-dependent interactions will be included since the model would otherwise suffer from overfitting due to too many covariates and the limited sample size.

Specific Aim 2: Following completion of Specific Aim 1, we expect to see significant acupuncture effect on the Median nerve (within each acupuncture group). In our proposed mixed linear model for Specific Aims 1 and 2 this would represent MM on the level of each individual group (MA, LF-EA, HF-EA). Conversely, we do not expect to observe a significant effect of acupuncture on the healthy Ulnar nerve as it is already functioning at optimal physiologic level. This would be the UU at the level of each individual group and corresponds to a clinical control. We will conduct direct contrasts between MM and UU as part of the mixed linear model with nerve location, time dependencies and random-effects grouping following the same design as in Specific Aim 1.

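### The location-by-time model on change scores cannot detect a carry-over that shifts both Week 2 readings equally, so it is not a full washout assessment

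*Combined protocol and SAP*

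**What the plan says.** Section 9.4 defines the exploratory washout model by its terms: "We will incorporate nerve location, evaluation time and the location-time interaction to check for dependencies between Week 1 and Week 2". It fixes the outcome: "the dependent outcomes of all models are the change in QST and NCS from baseline to post-acupuncture". It then claims: "This will allow for a full assessment of washout and carry-over effects". In the final model, time interactions are kept only if significant.

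The same section names other routes. One is a comparison of baselines: "Another way to characterize the wash-out effect of acupuncture is to compare baseline data from Week 1 and Week 2". Another is a persistence check: "Persistence of the acupuncture effects will specifically be assessed by comparing changes in outcomes after the first treatment but before the second session". Contrasts among the four reading times (before and after treatment in each week) are listed as secondary analyses. None of these is given a model, a comparator or a contrast by treatment order.

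On order, Section 9.4 says: "A time variable (Week 1, Week 2) will also be included to test for any effects due to order of the treated nerves". A later paragraph attaches order to the interaction instead.

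The protocol expects residual effects. Section 5.1.3 gives them as the reason for separating the two sessions. Section 5.2 collects a second baseline because "even a single intervention to PC3, PC5 or HT3, HT4 may alter NCS and QST parameters". Section 4.4 randomises order within each group, half to median first and half to ulnar first.

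**The concern.** Each change score is measured from its own session's baseline. The kind of carry-over the protocol anticipates in Section 5.2, a shifted Week 2 baseline, is the kind that this subtraction removes when the shift lasts through the session. A non-significant interaction could then be read as evidence of adequate washout when the test had no means of showing otherwise. The rule that keeps only significant time interactions would react to such a shift only by chance.

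The baseline comparison looks at the right quantity but is not specified. If it is run as a simple before/after comparison, a change over the week could be reported as persistence when it reflects practice or drift. Section 5.2 notes that subjects first meet the QST equipment at the Week 1 baseline.

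**Working it through.** The plan gives no figure for the washout analysis, so there is none to reproduce.

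**Inputs**
- Order: 60 subjects split 50:50 (Sections 4.4 and 9.1), so 30 per order, all assumed to have Week 2 data.
- Illustrative persisting effect: 0.35 °C, the CDT change in Section 9.1; also half (0.175) and double (0.70).
- SD of a within-nerve difference: Section 9.1 labels 0.696 as a variance, giving SD √0.696 = 0.834. The two SDs printed there, 0.9 and 0.4, pool to √((0.81 + 0.16)/2) = 0.696. Both values are run as a range.
- Assumptions: the SD of Week 2 minus Week 1 baseline equals the SD of the change; two-sided alpha is 0.05.

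**Step 1: algebra.** For a nerve treated in Week 1, let the carry-over be c_pre at the Week 2 baseline and c_post at the Week 2 post reading. Then

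Week 2 change = (post + c_post) − (pre + c_pre) = (post − pre) + (c_post − c_pre).

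Only c_post − c_pre survives. If the two are equal, nothing is left, whatever the sample size.

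**Step 2: simulation.** Two orders of 30, acute effect 0.35 °C, error SD per reading = SD of difference/√2, 4,000 runs per setting. Rejection rates are shown for SD 0.696 / 0.834. The second column is the 3-df location-by-time test on change scores. The third is a one-sample test of the treated-first nerve's baseline shift (n = 30). The fourth compares baseline shifts by order (30 vs 30, unadjusted).

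| Carry-over | Location × time | Before/after | By order |
|---|---|---|---|
| None | 5.2% / 4.9% | 5.3% / 5.4% | 5.1% / 4.8% |
| Stable 0.175 °C | 5.2% / 5.7% | 26.5% / 19.9% | 15.1% / 12.0% |
| Stable 0.35 °C | 4.8% / 5.4% | 75.8% / 59.9% | 47.5% / 36.7% |
| Stable 0.70 °C | 5.0% / 4.7% | 100% / 99.3% | 97.0% / 88.8% |
| 0.35 °C at Week 2 baseline, gone by post | 33.5% / 25.2% | 76.1% / 61.0% | 47.4% / 35.9% |

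Simulation error near 5% is √(0.05 × 0.95/4000) = 0.34 percentage points. The interaction column is flat at alpha for every stable shift and rises only when the Week 2 response changes. For the order contrast at 0.35 °C, an exact noncentral-t calculation gives 48% / 36%, and a separate run of 6,000 simulations gives 49% / 37%.

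**Step 3: drift.** The before/after test looks more powerful, but it cannot separate persistence from drift. With no persistence and an assumed drift of 0.2 °C common to both orders, it rejects in 33% / 24% of runs; with 0.1 °C, in about 12% / 10%. The order contrast stays at 5%, because the drift is the same in both orders and subtracts out.

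**Step 4: precision of the order contrast.** Half-width of the 95% interval = 2.00 × SD × √(2/30) = 2.00 × 0.696 × 0.258 = 0.36 °C, or 2.00 × 0.834 × 0.258 = 0.43 °C. An estimate near zero would still be compatible with full persistence of 0.35 °C.

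No power figure is given for conduction velocity. The SD in Section 9.1 (5.76 m/s) is the spread between patients, not that of a one-week difference within a subject.

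**The case against.** The strongest reply is that the plan does not rest on the change-score model alone. It names a baseline comparison, four-time-point contrasts and a persistence check, and Section 9.3 lists baseline and post values from both weeks as outcomes. That stands. A reader might infer that the whole washout assessment is blind to carry-over; the text does not support this, since a comparison of baselines can show a stable shift. What remains is that these analyses have no stated model or comparator.

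Second, Step 1 follows by construction, so the flat 5% adds no evidence about whether carry-over is in fact stable. That also stands. Where carry-over fades within the Week 2 session, the interaction test does respond.

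Third, it is tempting to call the baseline comparison uncontrolled and distorted by regression to the mean, because the Week 1 baseline is also the eligibility test. The documents do not say that it is uncontrolled: both nerves are measured in every subject, and a contrast by order is compatible with the wording. Eligibility removes subjects at both extremes (normal conduction and severe CTS; QST hypo- and hyperalgesia), so the net direction is unclear and no size can be given.

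Fourth, the plan has no rule that a null interaction is to be reported as absence of carry-over, and it calls these analyses exploratory. Both are true. They limit the weight of the point without making the claim of a full assessment correct.

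**Conclusion.** The claim of a full assessment is wrong for the location-by-time model on change scores. That model has no power beyond alpha for a carry-over of any size that is equal at the two Week 2 readings. It detects only carry-over that changes the Week 2 response: 25–34% of runs when 0.35 °C is present at the Week 2 baseline and gone by the post reading.

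A reader might infer that the treatment effects themselves are biased. By this route they are not: a stable shift cancels from the change-score contrasts, and re-measuring the baseline in Week 2 is what gives that protection. The defect is in what can be concluded about washout.

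The analyses that could show a stable shift need a contrast by randomised order to separate persistence from practice or time drift. The cancellation needs no distributional assumption. The power figures rest on 30 subjects per order and on the SD of the baseline difference equalling the plan's CDT SDs.

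**What to change.** For each nerve and outcome, regress the Week 2 baseline on the Week 1 baseline, randomised order (that nerve treated in Week 1: yes/no), age and gender. Report the order coefficient with its confidence interval as the persistence estimate. State that it measures persistence in the treated nerve relative to any persisting effect of treating the neighbouring nerve, because the comparison group had that other nerve needled in Week 1.

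Keep the location-by-time term on change scores only as a check for an altered Week 2 response. Describe the week main effect as a period effect: with order counterbalanced it does not test order. Delete the claim that the assessment is full, and state what each analysis can and cannot detect.

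The cost is SAP wording and one regression per nerve and outcome on data already collected. The drawback is modest power. For CDT, the unadjusted order contrast has about 36–49% power at a fully persisting 0.35 °C and about 12–15% at half that. The SAP should therefore say that a null result is not proof of washout.

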1. STUDY OBJECTIVES

1.1. Primary Objective

Specific Aim 1: Characterize the effects of acupuncture on QST (cold and vibration sensation thresholds) and nerve conduction study parameters in the Median and Ulnar nerves.

Hypothesis: Acupuncture will cause decrease in cold and vibration detection thresholds (improve sensation) in the underlying nerve sensory distribution only. Acupuncture will cause NCS changes, characteristic of improved nerve function.

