Specific Aim 2: For the current study, the Ulnar nerve is serving as a healthy control to allow for comparison to the diseased Median nerve post-intervention. Historic studies measuring the local, direct effect of acupuncture on a healthy nerve or studies comparing the local effects of acupuncture on a healthy versus a diseased nerve are not available. With respect to our Specific Aim 2 hypothesis, the Ulnar nerve is serving as a disease-free control condition, wherein acupuncture-dependent change in QST and NCS in the Ulnar nerve is anticipated to be largely negligible as the nerve is already functioning at optimal physiologic parameters. Due to this expectation of negligible treatment effect in the Ulnar nerve, the proposed sample size from Specific Aim 1 (20 subjects per acupuncture modality) is expected to be sufficient for these comparisons within each type of acupuncture. Further, we plan to carry out the Median/Ulnar nerve comparisons separately for each of the 3 intervention modalities. The use of both Median and Ulnar nerves lets the treatment as well as control conditions of interest come from the same subjects, allowing them to serve as their own controls. However, this repetition design warrants the use of mixed-model analysis so the random-effects portion can account for the intra-subject serial correlation expected with repeated measurements.

Specific Aim 3: With regards to the proper sample size for comparison among the 3 types of acupuncture – we based the sample size calculation for each study arm in part on the effect sizes observed by Lang et al (42), who enrolled 24 healthy subjects in 6 groups involving a cross over between manual, low-frequency and high-frequency acupuncture and were able to observe significant differences in QST (CDT) between the 3 acupuncture modalities, $p=0.0034$. In our current study, the cross-over design is based on the comparisons of Median and Ulnar nerves; however, the individual methods of acupuncture will be populated by different cohorts. For this reason, the random-effects blocking of our mixed- models will have the nerve dependence

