9.2. Stratified Randomization – See section 4.4

9.3. Outcome Measures and Statistical Hypotheses, as outlined in the Specific Aims

Specific Aim 1: Characterize the effects of acupuncture on QST (cold and vibration sensation thresholds) and nerve conduction parameters in the Median and Ulnar nerves.

Hypothesis: Acupuncture will cause decrease in cold and vibration detection thresholds (improve sensation) in the underlying nerve sensory distribution only. Acupuncture will cause NCS changes, characteristic of improved nerve function.

The outcomes generated in this aim will be the baseline and post-acupuncture values of CDT and VDT from Week 1 and Week 2, as well as baseline and post-acupuncture nerve conduction study data from both weeks, consisting of: distal motor/sensory latencies, CMAP and SNAP amplitudes, CMAP area and duration, nerve conduction velocities.

Specific Aim 2: Compare the effects of acupuncture on a diseased nerve (Median) to those of a healthy nerve (Ulnar), using QST (cold and vibration sensation thresholds) and NCS parameters.

Hypothesis: There will be greater change in cold and vibration detection thresholds and NCS parameters in the median nerve compared to the ulnar, due to the lower functional baseline of the median nerve.

The outcomes generated in this aim consist of statistical comparison of acupuncture-induced CDT, VDT and NCS changes in the Median nerve to those in the Ulnar nerve. The Post- minus Pre-acupuncture differences will be compared for the Median and Ulnar nerves in pooled data from all 3 groups, using independent sample t-testing.

Specific Aim 3: Compare the effects of manual acupuncture to those of low-frequency and high-frequency electroacupuncture.

Hypothesis: High-frequency electroacupuncture will have greater effect on NCS, QST followed by low-frequency electroacupuncture and manual acupuncture, in accordance to traditional practices. Acupuncture-induced changes in CDT, DVT and NCS parameters will be compared among the 3 groups (Post- minus Pre- changes), using ANOVA.

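### The plan expects the needled ulnar nerve to improve under Aim 1 but not to change under Aim 2, and it rests the Aim 2 sample size on the second expectation

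*Combined protocol and SAP*

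**What the plan says.** Write MM, MU, UM and UU for the four combinations of treated nerve (first letter) and tested nerve (second letter), as section 9.4 does.

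- **Aim 1 (sections 1.1, 3 and 9.3).** The hypothesis is "Acupuncture will cause decrease in cold and vibration detection thresholds (improve sensation) in the underlying nerve sensory distribution only". In section 9.3 the aim covers QST and "nerve conduction parameters in the Median and Ulnar nerves", so it applies to both nerves.
- **Section 5.2.** The Week 2 baseline is justified because, in the investigators' experience, "even a single intervention to PC3, PC5 or HT3, HT4 may alter NCS and QST parameters of the median and ulnar nerves, respectively".
- **Aim 2, formal hypothesis (section 9.3).** "There will be greater change in cold and vibration detection thresholds and NCS parameters in the median nerve compared to the ulnar".
- **Aim 2, sample size (section 9.1).** "acupuncture-dependent change in QST and NCS in the Ulnar nerve is anticipated to be largely negligible". The next sentence opens "Due to this expectation of negligible treatment effect in the Ulnar nerve" and concludes that 20 per modality should suffice for the median–ulnar comparison within each type of acupuncture.
- **Aim 2, analysis (section 9.4).** In each modality group a significant effect is expected in MM, but for UU "we do not expect to observe a significant effect of acupuncture on the healthy Ulnar nerve"; UU is described as a clinical control. A direct MM–UU contrast in the mixed model is planned. Section 9.3 instead names an independent-sample t-test on all three groups pooled.

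MM–UU is the only contrast between cells that is named. No margin or interval rule is given for a negligible effect or for the word *only* in Aim 1.

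**The concern.** When the Heart points are needled, the underlying nerve is the ulnar nerve, so Aim 1 predicts that UU improves. The Aim 2 text treats the same cell as a no-effect control. Nothing in the documents reconciles the two.

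Two things are at stake. First, the assumed zero in UU is the only argument for the Aim 2 sample size. If the ulnar nerve responds as Aim 1 predicts, the MM–UU difference shrinks and the argument fails. Second, the ulnar expectation is worded as absence of a significant effect at group level, where n is 20. A non-significant result there could be reported as a healthy nerve that does not respond when the data would also fit the full planned effect. Nerve specificity is the central question of the study, so the basis for such statements should be fixed beforehand.

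**Working it through.** **Inputs.** From section 9.1: variance of the CDT change 0.696 (°C)², assumed for both nerves, so SD = √0.696 = 0.834 °C; minimum change 0.35 °C; 20 per arm; α = 0.05; 80% power; motor NCV SD 5.76 m/s with a change of 3.7 m/s. Tests are taken as two-sided, since sidedness is not stated. The correlation ρ between the MM and UU changes within a subject is not in the documents; 0 to 0.7 is assumed.

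**1. The plan's own figure.** For a pre–post change, n = (SD × (1.960 + 0.842) / δ)².
- CDT: (0.834 × 2.802 / 0.35)² = 44.6, so 45 (47 with the t distribution). Power at n = 20 is 43%. The stated 20 per arm does not reproduce.
- NCV: (5.76 × 2.802 / 3.7)² = 19.0, so 20. This reproduces (78% power with the t distribution).
- √((0.9² + 0.4²)/2) = 0.696, using the two SDs that section 9.1 quotes. The figure may therefore be an SD labelled as a variance. Even then CDT needs 31.04, so 32. Both readings are carried below.

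**2. The MM–UU contrast for CDT.** SD of the difference = SD × √(2(1 − ρ)). Power comes from the noncentral t with n − 1 degrees of freedom and noncentrality δ√n / SD of the difference. For example, with SD 0.834 and n = 20:
- ρ = 0: SD of the difference 1.180, noncentrality 0.35 × 4.472 / 1.180 = 1.33, power 24%.
- ρ = 0.7: SD of the difference 0.646, noncentrality 2.42, power 63%.

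Taking the MM change as 0.35 °C, the ranges over ρ = 0 to 0.7 are:

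| | UU = 0 (difference 0.35) | UU = 0.175 (difference 0.175) |
|---|---|---|
| SD 0.834, n = 20 | 24–63% | 10–21% |
| SD 0.834, n = 60 | 62–99% | 20–54% |
| SD 0.696, n = 20 | 33–79% | 12–28% |
| SD 0.696, n = 60 | 77–99.9% | 27–70% |

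At n = 20 no entry reaches 80%, including the column where the ulnar effect is zero as the plan assumes.

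**3. Reading UU from its own test (CDT).** With SD 0.834, n = 20 and a true change of 0.35 °C, the noncentrality is 0.35 × 4.472 / 0.834 = 1.88. The probability of a non-significant result is then:

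| | True change 0.35 °C | True change 0.175 °C |
|---|---|---|
| SD 0.834, n = 20 | 57% | 86% |
| SD 0.834, n = 60 | 11% | 64% |
| SD 0.696, n = 20 | 43% | 81% |
| SD 0.696, n = 60 | 3% | 52% |

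The 95% CI half-width at n = 20 is 2.093 × 0.834 / 4.472 = 0.39 °C (0.33 °C with SD 0.696), about the size of the target effect.

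**4. NCV.** With SD 5.76, a true ulnar change of 3.7 m/s is missed 22% of the time at n = 20 and 0.2% at n = 60. MM–UU power for 3.7 m/s at n = 20 is 49–94% over the same correlations. The shortfall is thus mainly a CDT matter. The documents give no variance for VDT, so it cannot be checked.

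**The case against.** The strongest reply is that the formal hypotheses do not conflict. Aim 2 says that the median nerve changes more than the ulnar, not that the ulnar effect is zero, so a smaller positive UU satisfies both aims. This stands. The clash lies between the Aim 1 hypothesis and the Aim 2 expectation and sample-size premise.

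A reader might go further and infer that no UU result could count against the plan. The documents do not support that. A direct MM–UU contrast is planned, so UU at or above MM would count against Aim 2. A null UU counts against Aim 1 for the ulnar nerve, and worsening would contradict Aim 1.

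A reader might also infer that *only* in Aim 1 will be judged by non-significant tests in MU and UM, and that spill-over to the neighbouring nerve would usually be missed. The first is an inference from silence: the significance wording concerns UU, and the four-level factor can supply the contrasts needed. The second holds per modality or for a half-size effect. It does not hold for a full 0.35 °C effect pooled over 60, which is missed 11% of the time.

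Three smaller points also stand. Section 5.2 says only that values may alter, with neither direction nor size; this is in tension with a negligible effect but does not disprove it. Power for CDT is already short when UU is zero, so part of the shortfall is the separate CDT sample-size discrepancy. And section 9.4 labels the analyses exploratory, in a pilot study. None of this reconciles the two statements about UU or supports calling 20 per modality sufficient for CDT.

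**Conclusion.** The inconsistency is real and should be corrected. The documents predict that UU improves and also that it does not noticeably change, and the second prediction carries the Aim 2 sample size. For CDT the sufficiency statement is wrong as written: per-modality MM–UU power is 24–63% for 0.35 °C with no ulnar effect, and 10–21% if the ulnar nerve responds half as much. Reading 0.696 as an SD raises these to 33–79% and 12–28%, still below 80%. Pooled over 60 subjects with SD 0.834, the contrast has 62–99% and 20–54%. A non-significant UU in a single modality cannot establish that the healthy nerve does not respond.

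The figures assume two-sided tests, equal variance of change in both nerves (as section 9.1 does), complete data, an MM effect of 0.35 °C and correlations of 0 to 0.7. They do not include the covariates of the mixed model.

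**What to change.** 1. **One prediction for UU.** In sections 1.1, 9.1, 9.3 and 9.4, state an expectation that fits both hypotheses: an effect that may be positive but is smaller than MM, estimated two-sided with its confidence interval.
2. **Aim 2 sample size and test.** In section 9.1, delete the argument from a negligible ulnar effect to a sufficient sample, or make it explicitly conditional. Give MM–UU power per modality and pooled, over a range of correlations and with and without an ulnar response. Make the pooled within-subject MM–UU contrast in the mixed model the main Aim 2 test. The independent-sample t-test in section 9.3 gives up the within-subject pairing that section 9.1 presents as a strength.
3. **Nerve specificity.** Name the contrasts MM–MU, MM–UM, UU–UM and UU–MU from the existing four-level model and report the MU and UM intervals. Do not conclude effect in the underlying nerve alone, or no ulnar effect, from a non-significant P.
4. **Any equivalence margin** should be smaller than 0.35 °C. A margin of ±0.35 °C equals the whole target effect: at n = 60 and SD 0.834 the 90% CI half-width is 0.18 °C, so an estimated spill-over of 0.17 °C, about half the target, would pass as none.

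The cost is wording and a few contrasts, with no added subjects or visits. The downside is that the stated Aim 2 power becomes less favourable and per-modality claims of no ulnar effect become hard to make. As an illustration, 80% power to show equivalence within ±0.175 °C, when the true effect is zero, needs about 195 subjects (136 if 0.696 is an SD). With 60 subjects, such a claim would usually have to be reported as not shown.
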